### 1.0 PROTOCOL SUMMARY AND/OR SCHEMA

This will be a single center pilot study for 12 patients, designed to evaluate the efficacy of ribavirin monotherapy for patients with recurrent and/or metastatic (R/M) HPV-related malignancies. The study will be conducted in the Head and Neck Service.

Study subjects will self-administer ribavirin 1400 mg PO BID (total dose, 2800 mg/day). All patients will complete pill diaries to document administration of study drug. Cycle length is 28 days with continuous dosing.

Toxicities will be graded according to NCI CTCAE version 4.

Clinic visits for safety assessments and routine laboratory studies will occur weekly in Cycle 1, in weeks 1 and 3 of Cycle 2, and on Week 1 of subsequent cycles. Cross sectional imaging (CT or MRI) is obtained at baseline and q2 cycles and at End-of Treatment (EOT). Response assessments will follow RECIST 1.1 criteria.

Patients may remain on study until disease progression or unacceptable toxicity. Research biopsies at time of progression will only be obtained in subjects who have had an initial radiographic response.

## 2.0 OBJECTIVES AND SCIENTIFIC AIMS

Primary Objective: To obtain a preliminary efficacy assessment for ribavirin monotherapy among patients with R/M HPV-related malignancies

Secondary Objectives:

- (1) To describe overall survival and progression-free survival;
- (2) To describe the safety and tolerability of ribavirin in this patient population
- (3) To explore Gli-1 expression, as detected by immunohistochemistry (IHC) in pre-treatment archived pathology samples, as a candidate biomarker for efficacy of ribavirin in these cancers;
- (4) Among subjects who initially respond to ribavirin, to explore if subsequent acquired resistance is associated with increased Gli-1 expression.

## 3.0 BACKGROUND AND RATIONALE

[figure not shown]
Rationale for targeting eIF4E in HPV-related cancers

Viruses have developed myriad ways to co-opt the host cell protein translational apparatus in a way that favors virus production [1, 2]. In the case of high risk human papillomavirus (HPV) strains, this has oncogenic implications. The HPV E6 viral oncoprotein, in addition to its well-established interaction with p53, also directly activates cap-dependent protein translation. We propose that impinging on E6-driven aberrant cap-dependent protein translation represents a new line of attack against HPV-related cancers.

The key regulatory step in cap-dependent translation is the binding of eIF4E (eukaryotic initiation factor 4E) to the translation initiation complex [3]. Research interest in eIF4E in oncology began with the discovery by [name] (now at SKI) that eIF4E can function as an oncogene when it is overexpressed in a murine lymphoma model [4]. It is now apparent that elevated eIF4E expression is a characteristic of HPV-related cancers. Three clinical research teams have observed that eIF4E expression progressively increases with degree of cervical pathology along the continuum from normal cervical tissue, to cervical intraepithelial neoplasia (CIN)/dysplasia, and finally to invasive cervical carcinoma [5-7]. We also observed that elevated expression of phosphorylated eIF4E is a characteristic of HPV-related tonsil squamous cell cancer in retrospective tissue microarray analysis [8].

[figure not shown]
We propose that a positive feedback loop, centered at the level of protein translation, drives the expression of both E6 and eIF4E in HPV-related cancers. E6 stimulates the cap-dependent protein translation *in vitro* [9]. This effect of E6 on protein translation is a characteristic of high-risk oncogenic HPV strains. Potent stimulation of cap-dependent translation *in vitro* occurs with E6 protein from high-risk HPV16 and HPV18 strains and from low-risk HPV6b and HPV11 strains, but does not occur with E6 from non-oncogenic HPV5 and HPV8 [10] (Figure 1).

**Figure 1: Mucosal but not cutaneous HPV E6 proteins increase cap-dependent protein translation.** U2OS cells were transiently co-transfected with the pFR-CrPV-xb bicistronic luciferase reporter construct and expression vectors for high-risk mucosal HPV E6 proteins (HPV 16, HPV 18), low risk mucosal HPV E6 proteins (HPV6b, HPV 11), cutaneous HPV E6 proteins (HPV5, HPV 8), or empty vector (C) as control. The Y axis indicates the ratio (FF/Ren) of expression of Firefly (FF) reporter, which is cap dependent, to Renilla (Ren) reporter, which is cap-independent. (Spangle. JM, Ghosh-Choudhury, N., Munger, K. 2012 J Virol 86: 7466-7472) [10].

Because E6 is encoded on a capped mRNA [11], it is likely that there is a positive feedback loop in which expression of E6 and expression of eIF4E are mutually amplified (Figure 2). Additionally, there may be further positive feedback at the transcriptional level because E6 induces transcription of eIF4E in cell lines [5] (Figure 2).

**Figure 2: Proposed positive feedback loop between the HPV E6 oncoprotein and the m7G cap-binding protein eIF4E:** The E6 oncoprotein (pink) stimulates cap-dependent protein translation [9, 10], in which the binding of eIF4E to the m7G mRNA cap is a rate-limiting step [3]. Because E6 is encoded by capped mRNA [11], a positive feedback loop (solid arrowed lines) may be induced at the level of protein translation. There may also be a positive feedback loop at the transcriptional level due the ability of E6 to induce transcription of the eIF4E gene [5] (dotted arrowed lines).

#### Ribavirin is an antiviral agent that may be re-purposed for oncology due to eIF4E targeting

[figure not shown]
In 1972, the guanosine ribonucleotide analogue ribavirin (Virazole; 1-β-D-ribofuranosyl-1,2,4-triazole-3-carboxamide) was reported to have broad spectrum activity against both RNA and DNA viruses [12]. The most common adverse events associated with ribavirin are mild anemia, cough, and rash. For patients treated with prolonged ribavirin, anemia usually is mild and hemoglobin remains in the normal range [13, 14]. The combination of ribavirin + peginterferon α-2b has been approved by the Food and Drug Administration as effective treatment for chronic hepatitis C [15, 16].

In the otolaryngology literature, ribavirin is known to have activity against laryngeal papillomatosis (LP), a rare HPV-related disease in which the upper airway becomes progressively occluded with benign mucosal papillomas. Repeated laser surgery for removal of lesions has been commonly applied as a management strategy. In a small pilot study, patients (3 adults, 1 child) received pre-operative ribavirin (23 mg/kg daily) on the day of laser surgery, and continued oral ribavirin at the same daily dose for an additional 6 months (only 3 months for the child). The viral strain was HPV 6 in the papillomas of three patients, and was HPV 11 in one patient. Ribavirin treatment was associated a decrease in observable disease on follow up examinations, as determined by a previously described mapping score. Ribavirin treatment was associated with an increase in the time interval between successive required surgeries by a factor of at least 2 in all patients [17]. The efficacy of ribavirin against LP was confirmed in a subsequent case report [18], and ribavirin is considered to be one treatment option for this uncommon entity [19].

In 2004, [name] (now at SKI, but then working in the lab of [name]) published that ribavirin has anti-cancer activity pre-clinically that is directly related to eIF4E-targeting [20]. In xenograft experiments with an eIF4E-dependent head and neck SCC cell line (FaDu), ribavirin

[figure not shown]
treatment (40  $\mu$ g/kg daily) yielded tumor volume that was 6-fold less than in the untreated control group (Figure 3) [20]. [name] group subsequently studied ribavirin in M4/M5 acute myeloid leukemia (AML), another tumor type that is characterized by elevated eIF4E expression. In a proof of principle trial, ribavirin demonstrated encouraging activity, with 1 complete remission, 2 partial responses, 2 blast responses, 4 stable diseases, and 2 progressive diseases among 11 evaluable patients with M4/M5 AML. [21].

**Figure 3: Ribavirin activity against head and neck SCC xenograft.** Mean tumor volume in nude mice engrafted with cells derived from a head and neck SCC eIF4E-dependent tumor (FaDu) as a function of treatment with daily 1  $\mu$ M ribavirin orally at a dose of 40 $\mu$ g/kg per day (orange line) or control treatment (blue line). Photographs of tumors resected after 20 days of treatment (Kentis A, et al. 2004 PNAS 101: 18105-18110) [20].

[name] group has moved beyond the initial description of the anticancer efficacy of ribavirin in AML, to describe recently the most common mechanism of resistance to this drug: glucuronidation of ribavirin, mediated by the sonic hedgehog factor Gli-1 [22]. Ribavirin binds eIF4E in sensitive FaDu cells, but not in FRII cells with acquired resistance (Figure 4A). RNASeq demonstrates that ribavirin-resistant FRII cells have 21-fold elevation of Gli-1 [22]. Gli-1 upregulation leads to ribavirin glucuronidation. Pre-treatment of resistant cells with GDC-0449 (vismodegib, a small molecule inhibitor of sonic hedgehog signaling upstream of Gli-1) restored sensitivity to ribavirin (Figure 4B). Conversely, forced over-expression of Gli-1 in FaDu cells conferred resistance to ribavirin [22]. This mechanism also was observed in AML patients with acquired resistance to ribavirin in a phase II trial (NCT01056523; manuscript in preparation, [name], pers. comm.). These mechanistic insights into ribavirin resistance mechanism can inform the subsequent development of ribavirin in oncology.

**Figure 4.** Acquired Resistance to Ribavirin is associated with loss of ability of the drug to bind eIF4E. (A)  $^3$ H-Ribavirin co-immunoprecipitates (IPs) with eIF4E in FaDu cells, but not in cells with acquired resistance to ribavirin (FR II cells). GDC-0449 restores ability of  $^3$ H-Ribavirin to co-IP with eIF4E in FR II cells. (B) Cell growth of FR II cells and FaDu cells as a function of Gli-1 inhibition with 200nM GDC-0449 (courtesy of [name], adapted from: Zahreddine HA, et al Nature 2014 May 28 Epub ahead of print) [22].

Potential future implications: targeting eIF4E in combination therapy regimens

We now seek to develop ribavirin as an eIF4E-targeting strategy in HPV-related cancers. We envision that this approach could mature into future vertical inhibition strategies with other inhibitors of the PI3K/mTOR (phosphatidylinositol-3 kinase /mammalian target of rapamycin) pathway. eIF4E is downstream of mTOR in the PI3K/mTOR pathway, and there appears to be a convergence of molecular alterations on this pathway in HPV-related cancers. Mutations in *PIK3CA*, the gene encoding the catalytic subunit of PI3K, occur in approximately 25-30% of HPV related oropharynx cancers [23]. Cervical cancer studies have reported *PIK3CA* mutation rates of 14% to 31% [24, 25]. Although other anogenital cancers have been less well studied, one report demonstrated that *PIK3CA* hotspot mutations occur in 16% of anal cancers [26] and aberrant expression of eIF4E has been described in penile squamous cell cancer [27]. The convergence of molecular alterations along this pathway in HPV-related cancers suggests a strategy of blocking the pathway at upstream (PI3K) and downstream (eIF4E) locations.

The first-in-human trial of BYL719, an orally administered  $\alpha$ -specific PI3K inhibitor, provided encouraging results against HPV-related head and neck cancer. In this phase I trial for 72 patients with advanced solid tumors harboring *PIK3CA* alterations, 2 of the 3 best radiographic

[figure not shown]
responses in the study occurred in HPV positive head and neck cancers [28]. This phase I observation has prompted further study of BYL719 against head and neck cancers (MSKCC IRB 14-

116 and 14-021 [29]). It is likely that targeting PI3K may have useful activity against other HPV-related tumors as well. However, in order to obtain deeper and more durable responses, we anticipate that combination therapy strategies will be necessary. If ribavirin demonstrates clinically useful activity against HPV-related cancers, vertical inhibition to completely shut down the PI3K/mTOR/eIF4E axis in HPV-related cancers could be achieved by combining ribavirin with a PI3K inhibitor. In view of the central role that radiation therapy plays in the clinical management of HPV related cancers, future studies could also seek to build on the preclinical observation that targeting of eIF4E with ribavirin achieves radiosensitization against cancer cell lines [30].

## 4.1 OVERVIEW OF STUDY DESIGN/INTERVENTION

### 4.2 Design

This will be a single-institution pilot trial. The primary endpoint is to obtain a preliminary efficacy assessment for ribavirin monotherapy among patients with R/M HPV-related malignancies. There is no randomization or dose escalation.

### 4.3 Intervention

Subjects will self administer ribavirin 1400 mg PO BID (total, 2800 mg/day). Cycle length is 28 days with continuous dosing. Toxicities will be graded according to NCI CTCAE version 4. Clinic visits for safety assessments and routine laboratory studies will occur weekly in Cycle 1, in weeks 1 and 3 of Cycle 2, and on Week 1 of subsequent cycles. Cross sectional imaging (CT or MRI) is obtained at baseline and q2 cycles and at End-of Treatment (EOT). Response assessments will follow RECIST 1.1 criteria. Patients may remain on study until disease progression or unacceptable toxicity. At time of progression of disease, research biopsies will only be obtained in patients who had initial radiographic response.

## 5.0 THERAPEUTIC/DIAGNOSTIC AGENTS

### Ribavirin

#### *Availability and Administration:*

Generic ribavirin is commercially available as 200 mg, 400mg, and 600 mg tablets, which will be orally administered by the patients themselves. Ribavirin will be purchased from the hospital pharmacy. Tablets are supplied in bottles of 84 capsules (200 mg each). Ribavirin is available as blue-colored (shade depending on strength), capsule-shaped, film-coated tablets. Medication labels will comply with US legal requirements and be printed in English. The storage conditions for study drug will be described on the medication label. Ribavirin tablet should be taken with food (but it will not be considered a protocol violation if a subject takes dose on an empty stomach).

#### *Pharmacology:*

Ribavirin oral tablet administration is characterized by rapid absorption with a  $t_{max}$  of approximately 2 hours, followed by rapid distribution and long terminal phases. Mean  $\gamma$ -phase half-life has been reported to be in the range of approximately 30 - 61 hours after a single dose, and 274 - 296 hours following multiple doses. Mean bioavailability is approximately 30 - 50%. Apparent plasma clearance is approximately 20 L/h. Population based pharmacokinetic models have identified factors associated with lower apparent clearance of ribavirin (female gender, higher age, and low body weight), but taken together these factors account for less than 30% of the variability in clearance [31-34].

## 6.1 CRITERIA FOR SUBJECT ELIGIBILITY

### 6.2 Subject Inclusion Criteria

1. Recurrent and/or metastatic HPV-related carcinoma of the cervix, anus, vagina, vulva, penis, or oropharynx. The cancer diagnosis must be confirmed by slide review in the MSKCC Department of Pathology. HPV positive status must be demonstrated by HPV in situ-hybridization (ISH) and/or by p16 immunohistochemistry (IHC).  
Note: For cervix squamous cancer, HPV ISH test or p16 IHC test is not required, because all cervix squamous cancers are presumed to be HPV-associated.
2. Adults ( $\geq$  18 years of age)
3. ECOG performance status of 1 or better
4. Measurable disease according to RECIST 1.1 criteria
5. Availability of archived tumor tissue for correlative studies (5 unstained slides)
6. Adequate organ function, as follows:
  - Adequate bone marrow reserve: absolute neutrophil count (ANC)  $\geq$  1.5  $\times$  10^9/L, platelets  $\geq$  160  $\times$  10^9/L, hemoglobin  $\geq$  10 g/dL
  - Hepatic: total bilirubin within ULN (upper limit of normal); alkaline phosphatase (AP), aspartate transaminase (AST) and alanine transaminase (ALT)  $\leq$  2.0  $\times$  ULN
  - Renal: Serum creatinine  $\leq$  1.3 mg/dL. Patients with serum creatinine  $>$  1.3 mg/dL may be eligible if creatinine clearance (CrCl)  $\geq$  55 mL/min based on the standard Cockroft and Gault formula.
7. Ability to swallow oral medication.
8. Patients of childbearing potential must have a negative serum pregnancy test within 14 days of treatment. Patients must agree to use a reliable method of birth control during and for 6 months following the last dose of study drug.
9. At least one prior systemic therapy regimen for R/M HPV-related carcinoma

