## 10.0 EVALUATION DURING TREATMENT/INTERVENTION.

		Cycle 1	Cycle 2	Cycle ≥3	Post Treatment d
	Baseline	Weeks 1, 2, 3 and 4	Weeks 1 and 3	Week 1	
History and Physical	X	X	X	X	X
CBC, Comp panel	X	X	X	X	X
PT/aPTT	X				
Serum Pregnancy Test	X				
EKG a	X				
Radiologic Assessment (CT or MRI) b	X		X	X	
Archival Tissue	X				
Research biopsy c					X c
Adverse Event and Concomitant Medications Monitoring		Continuous Monitoring for Adverse Events			
Ribavirin		Continuous BID dosing			

a Baseline EKGs to be performed within 8 weeks prior to treatment

b Radiologic assessments occur at baseline (within 4 weeks of starting treatment) and q2 cycles. Imaging scans will be scheduled to occur in the last week ( $\pm$  2 days) of each even-numbered cycle. However, after completion of cycle 4, the interval between scans may be increased to q3 cycles, at the discretion of the investigator.

c Research biopsy at time of progression of disease is only for patients who experience initial radiographic response. When done, every effort should be made to obtain the research biopsy within 2 weeks of the last dose of ribavirin.

d The post treatment evaluation should occur 30 days ( $\pm$  1 week) after the last dose of ribavirin, for patients who maintain active follow up. The one exception is the post-treatment biopsy for patients who had previously responded (see footnote b)

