## 11.1 TOXICITIES/SIDE EFFECTS

### 11.2 General Considerations

#### Ribavirin Toxicities:

Hematologic: anemia, thrombocytopenia, leukopenia, lymphopenia

Gastrointestinal: anorexia, nausea, diarrhea

Hepatic: elevated liver function tests

Pulmonary: dyspnea, cough

Reproductive: may be teratogen

Constitutional: fatigue, musculoskeletal pain

Dermatologic: alopecia, pruritus, rash

Neurologic: headache, dizziness

Endocrine and metabolic: hyperuricemia

The listed ribavirin toxicities include those side effects described in the treatment of hepatitis C in which ribavirin may be given in combination with peginterferon alfa [13-16], and those side effects described in other settings including oncology research in which ribavirin was given at doses up to 1400 mg po BID [37][17, 21].

Even when the patient meets criteria for continued treatment at full dose per the protocol, the investigator retains the discretion to delay the next treatment and/or reduce ribavirin dose if there are safety concerns and/or logistical issues. Any dose reductions not specified in the protocol should be discussed with the principal investigator.

Doses that have been reduced for toxicity must not be re-escalated.

Treatment delays of up to 21 total days per cycle are allowed in a given cycle. Any patient who requires a treatment delay of >21 days, for medical and/or logistical reasons, in a given cycle should be removed from study.

If an investigator feels that a patient requires a dose reduction and/or dose delay other than those specified herein, this may be allowed after communication with the Principal Investigator, and would not be considered protocol violation. If the Principal Investigator is unavailable, Co-PI or designated covering investigator may address such issues as they arise.

Dose modification guidelines in this section are only for those adverse events thought to be at least possibly related to ribavirin.

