## 11.4 Renal Toxicity

If serum creatinine is  $\geq 1.5$  on planned treatment date, estimate the creatinine clearance (CrCl) by the Cockcroft and Gault Equation.

Calculated Creatinine Clearance (CrCl)	Management
$\geq 45$ ml/min	Hydrate as clinically indicated. May treat at full dose, treat at next lower dose level of ribavirin, or hold treatment, at the discretion of the investigator.
$< 45$ ml/min	Hold treatment for the week and hydrate as clinically indicated.  If repeat CrCl $\geq 45$ ml/min, may resume treatment at the next lower dose level of ribavirin

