### 11.7 Non-hematologic toxicity not otherwise specified

Dose delay and/or dose reduction is optional at the discretion of the investigator as regards the following  $\geq$  grade 3 adverse events: dental adverse events, hearing-related adverse events, INR or aPTT elevation, insomnia, weight gain or weight loss, SIADH, low bicarbonate, low albumin, hypophosphatemia. Similarly, the decision regarding whether to institute dose modifications for grade 2 or 3 fatigue will be at the discretion of the investigator.

For non-hematologic toxicity not otherwise specified:

$\geq$  Grade 3: Interrupt until resolved to  $\leq$  grade 1, then:  
If resolution to grade  $\leq 1$  in  $\leq 7$  days, resume ribavirin at the current dose level or at next lower dose level, at investigator discretion  
If resolution to grade  $\leq 1$  in  $> 7$  days, resume ribavirin at one lower dose level

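### Creatinine clearance is checked only when serum creatinine is above 1.3 mg/dL at entry or at least 1.5 on study, so some older, lighter patients with creatinine of about 1.0 to 1.3 can start full-dose ribavirin below 45 mL/min

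*Combined protocol and SAP*

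**What the plan says.** Section 6.2 (Subject Inclusion Criteria), item 6, gives two routes to renal eligibility. Creatinine of 1.3 mg/dL or less is enough by itself. Patients above 1.3 "may be eligible if creatinine clearance (CrCl") is at least 55 mL/min by Cockcroft-Gault. Sections 6.2 and 6.3 set no upper age limit and no minimum weight, and section 9.1 starts everyone at 2800 mg/day.

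On study, section 11.4 (Renal Toxicity) begins at creatinine of 1.5 or more. It gives no unit; mg/dL is assumed here. At that level staff are to act "on planned treatment date, estimate the creatinine clearance (CrCl) by the Cockcroft and Gault Equation". If the result is below 45 mL/min the instruction is "Hold treatment for the week and hydrate as clinically indicated", and once a repeat value reaches 45 the patient "may resume treatment at the next lower dose level of ribavirin". At 45 or above, the dose is left to the investigator.

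No other section asks for clearance. The section 10.0 schedule lists "CBC, Comp panel" at every scheduled visit, so the creatinine is always available.

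**The concern.** Serum creatinine depends on muscle mass as well as on kidney function, so the same value corresponds to a lower Cockcroft-Gault clearance in an older, lighter or female patient. The protocol limits clearance (55 mL/min at entry, 45 for a hold) but consults it only after creatinine passes a fixed level. The safeguard is therefore not evaluated in the patients whose creatinine looks acceptable because of age, sex and weight.

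Two things are at stake. A patient can begin the full dose at a clearance below the level at which section 11.4 stops treatment. And a fall below 45 that ribavirin may have caused can pass without any rule calling for a calculation. This is a question of patient safety and of a rule that misses its target. It does not touch the response criterion or the survival estimates.

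**Working it through.** The plan states no figure to reproduce here. The limits (1.3, 1.5, 55 and 45) come from sections 6.2 and 11.4. Ages and weights are assumptions, because the documents give no distribution of age, weight or creatinine.

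**Formula.** CrCl = (140 − age) × weight / (72 × creatinine), multiplied by 0.85 for women.

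**Entry.** Example, woman of 70 years, 50 kg, creatinine 1.3: 70 × 50 × 0.85 / 93.6 = 31.8 mL/min. All of the following are eligible with no clearance calculated:

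| Assumed patient | Creatinine 0.8 | 1.0 | 1.3 |
|---|---|---|---|
| Woman 60 y, 60 kg | 70.8 | 56.7 | 43.6 |
| Woman 65 y, 55 kg | 60.9 | 48.7 | 37.5 |
| Woman 70 y, 50 kg | 51.6 | 41.3 | 31.8 |
| Woman 75 y, 50 kg | 48.0 | 38.4 | 29.5 |
| Man 70 y, 60 kg | 72.9 | 58.3 | 44.9 |
| Woman 45 y, 70 kg | 98.1 | 78.5 | 60.4 |
| Man 70 y, 80 kg | 97.2 | 77.8 | 59.8 |
| Man 45 y, 50 kg | 82.5 | 66.0 | 50.7 |

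The last three rows vary one factor at a time, and none falls below 45. In the first five, all are below 45 at creatinine 1.3, two of five at 1.0, and none at 0.8. At 0.8 a more extreme patient is needed, such as a woman of 75 years and 45 kg (43.2).

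**Weight below which clearance is under 45.** Weight = 45 × 72 × creatinine / (140 − age), with the denominator multiplied by 0.85 for women.

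- Creatinine 1.3: women 61.9 kg at 60 and 70.8 kg at 70; men 52.7 and 60.2 kg.
- Creatinine 1.0: women 47.6 and 54.5 kg; men 40.5 and 46.3 kg.

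**Ordering of patients.** A man of 50 years and 60 kg with creatinine 1.4 has 90 × 60 / 100.8 = 53.6 mL/min and is refused (below 55). A woman of 75 years and 50 kg with creatinine 1.3 has 29.5 and is accepted.

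**On study.** Woman of 60 years, 60 kg: 80 × 60 × 0.85 / 72 = 56.7 at creatinine 1.0, and 56.7 / 1.4 = 40.5 at 1.4. She crosses 45 at creatinine 56.7 / 45 = 1.26, so from there to just under 1.5 the hold would apply on clearance but is never assessed.

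**The case against.** The strongest reply is that section 11.4 manages toxicity and does not set a standing floor. Section 11.2 confines the dose-modification rules to adverse events that ribavirin may have caused. A stable baseline clearance of 40 is not an adverse event, so a reader who infers that the protocol's own hold already applies to such a patient on day 1 goes too far. That stands. The case at entry is that the protocol's two renal limits leave a group unexamined; the case on study concerns falls possibly due to the drug, as in the rise from 1.0 to 1.4.

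A reader might also infer that the protocol is silent when clearance stays below 45. It is not: sections 11.2 and 13.0 remove a patient who needs a delay of more than 21 days in a cycle.

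Nor do the documents show harm. They do not state that ribavirin is cleared by the kidney. Section 5.0 links female sex, higher age and low weight to lower apparent ribavirin clearance, but adds that "taken together these factors account for less than 30% of the variability in clearance". Anemia, the most common reason for dose reduction, has its own rule in section 11.3; Cycle 1 visits are weekly; the investigator may reduce or delay at any time; and exclusion 3 in section 6.3 bars serious medical conditions. These protections are real. However, none of them prompts a clearance calculation, and the hemoglobin rule acts only after toxicity has appeared.

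Finally, requiring 55 mL/min of everyone would exclude more patients than a concern about values below 45 supports, since section 11.4 permits full dose between 45 and 55 even at creatinine of 1.5 or more. That also stands and shapes the fix.

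**Conclusion.** The point holds in a limited form. The creatinine thresholds leave the protocol's clearance limits unevaluated in patients who combine older age, low weight, usually female sex and creatinine of about 1.0 to 1.3. In the assumed examples such patients enter at roughly 30 to 45 mL/min, and a possibly drug-related fall below 45 can go unnoticed.

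Age, weight and sex without a creatinine in that range are generally not enough, as the 0.8 column shows. The conclusion rests on Cockcroft-Gault, which the protocol names, and on assumed ages and weights. It gives no prevalence: the number among 12 could be zero. The size of any increase in exposure or toxicity cannot be derived from the documents. The change is worth making because it is cheap and reuses limits that the sponsor has already chosen.

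**What to change.** 1. **Section 6.2, item 6.** Calculate Cockcroft-Gault clearance for every patient at entry and admit nobody below 45 mL/min, whatever the creatinine. Keep the 55 limit for creatinine above 1.3.

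2. **Section 11.4.** Calculate clearance from the chemistry already drawn at each scheduled visit, using current weight. Apply the below-45 hold whatever the creatinine when the fall is possibly due to ribavirin. Where weight loss alone explains the fall, use investigator review instead of an automatic hold and reduction. Section 11.7 already leaves action on severe "weight gain or weight loss" to the investigator, and a reduction is permanent under section 11.2: "Doses that have been reduced for toxicity must not be re-escalated". Keep the present discretion at creatinine of 1.5 or more with clearance of at least 45.

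**Cost.** Wording in two sections, a weight at each visit and a short calculation. Some older, lighter patients become ineligible: at creatinine 1.0, women under about 48 kg at 60 or 54.5 kg at 70; at 1.3, under about 62 or 71 kg. With accrual of 1 to 2 per month this could slow a 12-patient pilot slightly. There may also be a few more holds, because a patient admitted at 50 reaches 45 with a creatinine rise of 11% (50/45 − 1).

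The sponsor could instead require 55 of everyone. The margin would then be a 22% rise (55/45 − 1), but a woman would need about 58 kg at 60 or 67 kg at 70 with creatinine 1.0, and about 76 or 87 kg with 1.3.
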